10.1 Disposition of Participants and Discontinuations

Subject disposition will be presented for the ES:

- Total number of subjects enrolled (i.e. subjects who gave informed consent),
- Number of subjects who discontinued from the study prior to treatment overall and grouped by the main reason (i.e. the Reason why the subject did not continue beyond screening as recorded in the CRF. If the Subject did not meet all Eligibility Criteria the failed specific inclusion or exclusion criteria will be provided in addition). Subjects not classified as screened failure but without treatment assignment by the iRT will be listed as “no treatment assigned”,
- Number of eligible subjects (i.e. subjects with treatment assignment by the iRT system),
 - overall and by Treatment Course, who received at least one dose of study medication,
 - who discontinued the study medication, grouped by main reason (reason from last treatment stopped),
 - who discontinued/completed the study (according to the information on the Study Termination CRF page).
- Number of visits performed before and after Start of COVID-19 pandemic
- MSQoL-54 completion status, including reasons for missing data

Percentages will be presented with respect to the number of eligible subjects.

The number of subjects in each analysis set will be provided overall, by region, by country within region and by site.

The following subject data listings will be provided:

- Listing of discontinued subjects for the ITT,
- Listing of subjects excluded from the Analysis Sets.

10.2 Protocol Deviations

10.2.1 Important Protocol Deviations

The following summary tables and listings of major protocol deviations (see Section 8.1 for details) will be provided by Inclusion/Exclusion and other deviations for the ITT:

- Frequencies per reason of major protocol deviations (overall and based on relationship to COVID-19 pandemic),
- Listing of major protocol deviations (including information regarding relationship to COVID-19 pandemic).

11 Demographics and Other Baseline Characteristics

If not stated otherwise, summaries will be presented on the FAS.

11.1 Demographics

Demographic characteristics will be summarized using the following information from the Screening/Baseline Visit CRF pages.

Demographic characteristics

- Gender:
 - Male,
 - Female,
 - Missing.
- Race:
 - White,
 - Black or African American,
 - Asian,
 - American Indian or Alaska Native,
 - Native Hawaiian or Other Pacific Islander,
 - Other,
 - Not collected at this site,
 - Missing.
- Ethnicity:
 - Hispanic or Latino,
 - Yes,
 - No,
 - Missing.
 - Japanese,
 - Yes,
 - No,
 - Missing.
- Age (years)

- Age categories:
 - ≤ 40 years,
 - >40 years, <65 years,
 - ≥ 65 years,
 - Missing.
- Region:
 - Eastern & Central Europe:
 - (Austria, Hungary, Lithuania, Poland, Slovakia, Czech Republic)
 - Scandinavia:
 - (Denmark, Finland, Norway, Sweden)
 - Southern Europe:
 - (Greece, Italy, Portugal, Spain)
 - Western Europe:
 - (Belgium, France, Netherlands, United Kingdom)
 - Australia
- Pooled Center
 - Defined pooled center.
- Country
 - Country 1
 - ...

The following subject data listing will be provided:

- Demographic Data (Country, Sex, Race, Age, EDSS at Baseline, Number of relapses during last year).

11.2 Medical History

The medical history will be coded using the Medical Dictionary for Regulatory Activities (MedDRA) in the latest available version. Summary table will be presented by primary system organ class (SOC) and preferred term (PT).

11.3 Other Baseline Characteristics

MS Disease Characteristics

The duration since onset and diagnosis of MS at Baseline in months, the number of previous DMDs as well as the EDSS at Baseline will be presented. In addition, the number of subjects grouped by the major system affected (at onset of MS) will be presented.

- Time since onset of MS (months) = (visit start date of Baseline Visit - date of first symptom + 1) / 30.4375,

- Time since Diagnosis (months) = (visit start date of Baseline Visit - date of diagnosis + 1) / 30.4375,
- Time since first relapse (months) = (visit start date of Baseline Visit - date of first relapse + 1) / 30.4375,
- Number of previous DMDs (i.e. number of different PTs of DMDs as entered into the "Relevant Previous Medication Form" (Appendix 1)):
 - 0
 - 1,
 - 2,
 - >2,

MRI Disease Characteristics

The following Screening MRI results will be presented:

- Number of T1-Gd+ enhancing lesions,
- Number of T1-Gd+ enhancing lesions:
 - 0,

- > 0 ,
- Non-evaluable
- Missing
- Total number of T2 lesions,
- Total number of T2 lesions:
 - 0,
 - 1 - 8,
 - ≥ 9
 - Non-evaluable
 - Missing
- Total T2 lesion volume (cm³),
- Brain volume (cm³),
- Grey matter volume (cm³),
- White matter volume (cm³),
- Deep grey matter volume (cm³).

Vital Signs

The following Baseline characteristics will be provided in summary tables:

- Height, weight, body surface area, body mass index,
- Body temperature, heart rate, Systolic Blood Pressure, Diastolic Blood Pressure.

The body surface area (BSA) and body mass index (BMI) will be calculated with the following equations:

- $BSA(m^2) = ([height(cm) * weight(kg)] / 3600) ^ 0.5$
- $BMI (kg/m^2) = [weight (kg) / height (cm)^2] * 10000$

12

Previous or Concomitant Medications/Procedures

Concomitant medications are medications, other than study medications, which are taken by subjects during the study.

Concomitant medications will be summarized from the “Concomitant medication” eCRF page. ATC-1st level and preferred term will be tabulated as given from the WHO-DD dictionary current version. In case multiple ATC’s are assigned to a drug, all ATC-1st level will be used for reporting. All medications entered into the “Concomitant medication” eCRF page will be assumed to be “concomitant” irrespective of the actual start and end dates. In addition, all concomitant medications as well as concomitant medications given for disease related conditions will be presented by PT and by decreasing frequency.

Relevant previous medications are medications, other than study medications, which stopped before enrolment (i.e. date of informed consent [IC]). DMDs (see Section 8.2) administered between IC and start of study medication are major PDs that will be reported as relevant previous medications as well.

Relevant previous medications will be summarized from the “Relevant previous medication details” eCRF page. ATC-1st level and preferred term will be tabulated as given from the WHO-DD dictionary current version. In case multiple ATC’s are assigned to a drug, all ATC-1st level will be used for reporting. All medications entered into the “Relevant previous medication details” eCRF page will be assumed to be “previous” irrespective of the actual start and end dates. In addition, all relevant previous medications and relevant previous medications given for disease related conditions will be presented by PT and decreasing frequency.

All relevant previous medications, which are classified as DMDs will be presented by PT. DMDs, which are taken within 6 months prior to start of study medication (i.e. DMD end date \geq start of study medication – 182.625) will be presented by PT. The length of the washout period (start of study medication - DMD end date + 1) of the last DMD within 6 months prior to start of study medication will be summarized. The last DMD will be defined as the DMD with the latest stop date. If the DMD end date is partially missing, the day will be imputed by the 15th of the month but the date will be truncated to IC date -1 if the imputation results in a later date of the same month when the IC was provided. If the month is missing as well or the date is completely missing the end date will not be replaced and it will be assumed that the DMD stopped earlier than 6 months prior to start of study medication.

Concomitant procedures which were undertaken any time on study will be listed by subject.

13 Treatment Compliance and Exposure

Two years of treatment are planned in this study. Subjects will take tablets in week 1 and week 5 of each year. All dosing calculations and summaries will be based on "Treatment Administration" and "Treatment Termination" eCRFs pages.

The following summary tables will be provided for the SAF:

- Duration of therapy
- Compliance and Drug Accountability

The duration will be presented for Treatment Course 1 Treatment Period, Course 2 Treatment Period and the Treatment Period in days.

- Duration (days)= (date of last tablet in period – date of first tablet in period + 1)

Counts of tablets and compliance will be calculated first for each treatment week:

- Compliance (%) = $100 * \text{number of tablets taken during the treatment week} / \text{number of planned tablets for the treatment week}$

If a subject discontinued the treatment before the start of the respective treatment week, compliance will not be derived for this week. If the subject did not take any tablet during the respective treatment week, but had not discontinued the treatment before, compliance will be 0. If the subject was treated during the respective treatment week, but the number of tablets is unknown, compliance will be missing.

Compliance for each year (course) and total will be calculated for all subjects that started the respective treatment period (i.e. taken at least one tablet) as an average of available records obtained for the corresponding treatment weeks. That means, treatment weeks after the subject's treatment discontinuation are not included in the derivation, records of 0 compliance for the corresponding treatment weeks are included in the derivation as such, and missing records result in missing compliance for the respective treatment period.

In addition, compliance will be categorized as follows:

- < 60%
- [60%-80%[
- [80%-90%[
- [90%-110%]
- > 110%
- Missing

The number of planned tablets is based on the weight at the beginning of each treatment course (Table 3).

Table 3: Dose of Mavenclad® per treatment week by subject weight in each treatment year

Weight range kg	Dose in mg (number tablets) per treatment week	
	Treatment week 1	Treatment week 5
40 to <50	40 mg (4 tablets)	40 mg (4 tablets)
50 to <60	50 mg (5 tablets)	50 mg (5 tablets)
60 to <70	60 mg (6 tablets)	60 mg (6 tablets)
70 to <80	70 mg (7 tablets)	70 mg (7 tablets)
80 to <90	80 mg (8 tablets)	70 mg (7 tablets)
90 to <100	90 mg (9 tablets)	80 mg (8 tablets)
100 to <110	100 mg (10 tablets)	90 mg (9 tablets)
110 and above	100 mg (10 tablets)	100 mg (10 tablets)

The number of subjects with the same planned dosing schema in both Treatments Courses and a different planned dosing schema (i.e. subjects exchanged weight range as defined in the table above) in Treatment Course 2 will be presented for all subjects, who have started Treatment Course 2 (i.e. taken at least one tablet in Treatment Course 2).

The time difference between the start of the Course 1 Treatment Period and the start of the Course 2 Treatment Period will be calculated as follows:

- Relative Start of Treatment Course 2 (days) = Start of Treatment Course 2 - Start of Treatment Course 1 +1.

The Relative Start of Treatment Course 2 will be presented together with the number of subjects in the following groups for the SAF:

- Treatment Course 2 not started,
 - and discontinued before the Month 12 Visit,
 - and discontinued at or after Month 12 Visit
 - Lymphocyte count < 800 cells/mm³ at Month 12 Visit,
- Treatment Course 2 started,
 - and not delayed (see Section 9 for definition),
 - and delayed,
 - and any Lymphocyte count < 800 cells/mm³ at or after Month 12 Visit and before start of Treatment Course 2.
 - before / after Start of COVID-19 pandemic

The cumulative dose is defined as the sum of the number of tablets taken 10 mg divided by the weight for each treatment year:

- Cumulative dose = number of tablets taken in Treatment Course 1 * 10mg / weight in kg at Baseline + number of tablets taken in Treatment Course 2 * 10mg / weight in kg at Month 12b

The cumulative dose will be calculated only if the weight and number of tablets are available. Otherwise it will be missing. If the Treatment Course 2 wasn't started (i.e. no tablet taken in Treatment Course 2), the cumulative dose will be calculated only for the Treatment Course 1.

A subject data listing of the treatment compliance will be provided for the SAF.

14 Efficacy Analyses

The following sections describe the planned analyses for each efficacy endpoints.

For the detailed definition of covariates and stratification factors that are used in the statistical models see Section 9.

Descriptive summary statistics will be presented for the absolute values and the changes from baseline as applicable, for each visit and for all efficacy endpoints for the FAS. Details about the presentation of continuous and qualitative variables are given in Section 9.

Wherever possible, all estimated results from the statistical models will be calculated with the same observed margin which reflects the population of the whole corresponding analysis set, regardless of missing data.

14.1 Primary Endpoints: Changes in MSQoL-54 physical and mental health composite scores from Baseline to Month 24 Visit

The primary endpoints are the changes in MSQoL-54 physical and mental health composite scores at Months 24 Visit compared to Baseline.

The MSQoL-54 is a multidimensional health-related quality of life measure that combines both generic and MS-specific items into a single instrument (Vickrey et al., 1995; Vickrey et al., 1997). The MSQoL-54 questionnaire was developed to measure HRQoL in subjects with MS. It is composed of 54 items and is a combination of the SF-36 as well as an additional 18 disease-specific items such as fatigue and cognitive function.

The questionnaires will be summarized in 5 (composite) scores

- Physical health composite,
- Mental health composite,
- Satisfaction with sexual function,
- Change in health,
- Overall quality of life,

which will be derived from the 12 subscales (Physical function, Role limitations-physical, Role limitations-emotional, Pain, Emotional well-being, Energy/fatigue, Health perceptions, Social function, Cognitive function, Health distress, Overall quality of life, Sexual function) following the rules specified in the Scoring Manual (Vickrey 1995). All scores range from 0% to 100%. 100% is the best possible score.

The primary analysis is focusing on the physical and mental health composite scores while the overall quality of life will be analyzed as a tertiary endpoint. The other composite scores and subscales will not be analyzed statistically.

The observed results and changes from Baseline will be tabulated and plotted for Physical health composite, mental health composite and Overall quality of life for the FAS. In addition, the estimated Least Square (LS) Means of the change from Baseline with the corresponding standard error, 95% confidence interval and two-sided p-value of the analysis model (see Section 14.1.1) will be summarized and plotted.

The Overall quality of life, Physical and Mental health composite scores and the change from Baseline of the MSQoL-54 will be listed by subject.

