6.5.4.1 Switching from Other DMDs

For the subjects switching from another DMD, the mode of action and duration of effect of the current, or previous DMD should be considered prior to initiation of Mavenclad®. In such cases, it is at the Investigator's discretion to define the required time interval between completing the previous treatment and initiating Mavenclad® treatment. This decision must be based upon the respective treatments' European Medicines Agency SmPC*, independently published guidelines (i.e. Kompetenznetz Multiple Sklerose [KKNMS]) and standards of care

* The washout period/ time to wait before switching from one DMD to another, can be described in the product characteristics of the respective drug."

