The start of COVID-19 pandemic will be defined by country as the earliest date of either the date of the first death from COVID-19 occurred in each country according to the published data by European Centre for Disease Prevention and Control on 26th June 2020 (<https://www.ecdc.europa.eu/en/publications-data/download-todays-data-geographic-distribution-covid-19-cases-worldwide>) or 11th March 2020 (when the WHO declared COVID-19 pandemic).

Visit timing with respect to COVID-19 pandemic

A visit is defined to be performed after the start of COVID-19 pandemic if the visit end date is greater than the start of COVID-19 pandemic date.

Conversion factors

The following conversion factors will be used to convert days into months or years for all observations except Visit related dates:

- 1 month = 30.4375 days,
- 1 year = 365.25 days.

Time window

- Day 1 is the day of start of study medication, the day before is Day -1 (no Day 0 is defined).
- Study day / Treatment day is defined relative to Day 1.

The visit schedule is defined as follows:

- 1 month = 30 days,
- 1 year = 360 days,

relative to the start date of the Baseline Visit for Treatment Course 1 and relative to the start date of the Month 12b Visit as defined in the eCRF (see also Section 15.3) for Treatment Course 2.

In each analysis, should assessment be delayed, subjects' assessment data will be treated as though it occurred at the time point specified (i.e. out of visit windows will be not excluded or adjusted for any analyses) and inferences will be conducted accordingly. Thus, further time windows will not be specified.

All observations from unscheduled Visits will be included only in the analyses of Visit independent summaries (e.g. counts of events, progressions or worst value during Treatment Period) unless for the last assessment available. In this case the missing ET visit will be imputed by the unscheduled visit.

If not specified otherwise, the assessments of the ET visit will be mapped to the nearest next planned post-baseline visit with a missing assessment before or after the ET visit of the individual assessment for all statistical analyses and descriptive summaries. As not all assessments of the ET

are performed at each visit, the different assessments of the ET can be assigned to different visits. If the duration (in days) between the ET visits and two missing planned visits are equal, then the assessment will be assigned to the later visit.

Handling of missing data

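### SAP Section 12 counts a DMD with a missing end month as stopped more than 6 months before dosing, even when the recorded year rules that out

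*SAP*

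**What the plan says.** SAP Section 12 plans two descriptive outputs on recent prior treatment. The first is a table of DMDs taken within 6 months before first dose, defined as an end date on or after "start of study medication – 182.625". The second is a summary of washout length for the last DMD in that window, computed as "start of study medication - DMD end date + 1". The last DMD is the one with the latest stop date.

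Incomplete end dates are handled in two ways:

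- **Day missing only:** "the day will be imputed by the 15th of the month but the date will be truncated to IC date -1". The truncation applies only when the imputed date falls too late in the month of informed consent. There is no equivalent limit at first dose.
- **Month missing, or whole date missing:** nothing is imputed. Instead, "it will be assumed that the DMD stopped earlier than 6 months prior to start of study medication".

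The same section keeps DMDs given between consent and first dose in these outputs and classes them as major protocol deviations. SAP Section 9 (handling of missing data) only refers back to Section 12 for DMD end dates.

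Protocol 6.5.4.1 leaves it to the investigator "to define the required time interval between completing the previous treatment and initiating" the study drug.

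**The concern.** A missing-data rule should not contradict what was recorded. When only the year is known, that year can settle whether the drug was stopped recently, and the SAP discards it. The SAP does use the year elsewhere: its rules for partial relapse onset dates (Section 9) and partial adverse event onset dates (Section 15.1) compare the known year with the year of first dose.

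The outputs matter for describing the population. One of the two eligibility routes in Protocol 5.3.1 requires a relapse while on another DMD, and the switching interval is set case by case. These two outputs are the SAP's planned account of how recently subjects had been treated. Relevant previous medications are also part of both interim analyses (SAP 6.1.1 and 6.1.2).

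The second gap is the missing limit at first dose for an imputed 15th. It can produce a washout that is impossible on its face.

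**Working it through.** **The plan's own figure.** SAP Section 9 gives "1 month = 30.4375 days". Six months are 6 × 30.4375 = 182.625 days, which matches the window in Section 12.

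**Year-only dates, end year equal to dosing year.** The earliest possible end date is 1 January. A record is certain to be within 6 months if first dose minus 1 January is at most 182.625 days.

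- 1 January to 1 July is 31 + 28 + 31 + 30 + 31 + 30 = 181 days, or 182 in a leap year. Both are inside the window.
- In a non-leap year 2 July (182 days) also qualifies. 1 July holds in every year.
- Example: end date '2019', first dose 15 May 2019. The longest possible gap is 31 + 28 + 31 + 30 + 14 = 134 days, yet the rule treats the drug as stopped more than 6 months earlier.
- For later first doses the year no longer settles the matter. Of the possible end dates from 1 January 2019 to the day before dosing, 182 of 273 (66.7%) are within the window for a first dose on 1 October, and 182 of 364 (50%) for 31 December.

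**Year-only dates, earlier end years.** Here the rule is sometimes right.

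- End year one before the dosing year, first dose 2 July 2019: the latest possible end date is 31 December 2018, which is 183 days before and outside the window. The SAP's assumption is correct.
- Same, first dose 1 March 2019: 31 August to 31 December 2018 is inside the window, 123 of 365 dates (33.7%). This cannot be determined.
- End year two or more before the dosing year: the gap is at least 366 days, so the assumption is correct.

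**Effect on the last DMD.** A record with no usable stop date cannot be the latest. Take DMD A stopped 15 October 2018, DMD B with end date '2019', and first dose 1 March 2019.

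- Reported washout, based on A: 137 + 1 = 138 days.
- Possible washout for B, stopped between 1 January and 28 February: from 1 + 1 = 2 to 59 + 1 = 60 days.

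**Missing day with no limit at first dose.** Consent 20 May, first dose 10 June, end date 'June'. The imputed end is 15 June. It is not truncated, because June is not the consent month. Washout = 10 − 15 + 1 = −4 days. A DMD stopped from 1 to 9 June would give 10 to 2 days on the same formula. With first dose on the 2nd of the month the result is 2 − 15 + 1 = −12 days. The record still passes the 6-month test, because that test has no upper limit.

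**The case against.** Several arguments on the other side stand.

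- **Nothing inferential depends on these dates.** The DMD pre-treated/naïve subgroup (SAP 8.2) uses any DMD at any time before dosing, and the primary MSQoL-54 model (SAP 14.1.1) contains no DMD date.
- **Year-only dates may be uncommon for recent switches.** The investigator has to weigh the previous DMD before starting (Protocol 6.5.4.1). A screening extension for washout needs advance written approval from the Medical Monitor (Protocol 7.1.1). Screening scans of subjects switching from PML-linked drugs go to a central reader (Protocol 7.3.5.3.3). Recent stop dates are therefore likely to be better documented than old ones.
- **The negative washout is a corner case.** It needs a DMD continued past consent (a major deviation), a missing end day, an end month after the consent month, and a first dose before the 14th of that month.

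Three stronger readings might be inferred, but the documents do not support them.

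- *The '+1' in the washout formula inflates washout and understates recent use.* The '+1' is the SAP's general duration convention (Section 9), also used for time since onset and duration of therapy. It shifts every subject equally, and the 6-month test uses the plain date limit, so it cannot move a record in or out. Replacing it with '−1' would give −1 day for a DMD stopped on the day of first dose.
- *Negative washouts understate recent use.* They do not, since the record still counts as within 6 months.
- *Records with a missing month appear in a long-washout category.* Section 12 plans no such row. The records are simply absent from the 6-month table and the washout summary, so washout is overstated only where an older DMD takes the place of the true last one.

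**Conclusion.** The point holds as a minor one. The missing-month rule gives a demonstrably wrong classification whenever the end year is the dosing year and first dose is between 1 January and 1 July. For other dates it is sometimes right and sometimes an unsupported guess. The error from this rule runs one way: it can drop recent users but never add them. That statement does not extend to the 15th-of-month rule, which can misplace a record in either direction near the 6-month limit.

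The absence of a limit at first dose is a separate, smaller gap. It yields impossible values, is probably rare, and does not affect the classification.

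The range from 1 January to 1 July is about half the calendar, which is a share of first-dose dates and not of subjects. The documents do not say how many DMD end dates are partial, so the size in subjects cannot be given. The calculations take the SAP text literally and assume that a previous DMD ended no later than first dose. The impact is confined to the descriptive prior-DMD and washout outputs.

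**What to change.** In SAP Section 12:

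- **(a) Year-only end dates.** Take the earliest and latest possible end dates in the recorded year, the latest being no later than first dose. Classify the record as within 6 months if all possible dates are within 182.625 days, as earlier if none are, and as 'unknown' otherwise. Show completely missing dates as 'unknown'. This matches the default in SAP Section 9 of presenting missing observations as a separate category. Year-only dates that are provably older stay classified as older. Where a year-only record could be the last DMD, show its washout length as unknown and do not take it from an older drug.
- **(b) Missing day.** Cap the imputed end date at first dose − 1 day. In the example above this gives 9 June and a washout of 2 days. If first dose is on the 1st of the recorded end month, the cap would contradict that month, so query the record.
- **Keep the '+1'** in the washout formula.

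The cost is a few lines of SAP text, minor programming and one added 'unknown' row in the table. No primary or secondary analysis changes.
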